#### **4.4.2 Baseline**

For the evaluation in the treatment-naïve population, the baseline measurement is the latest non-missing observation before the first dose of study medication. For the evaluation in the anti-VEGF–incomplete-responder population, the baseline is the observation from Study Week 12. If the week 12 observation is missing, the patient will not be included in the incomplete responder population. For patients who did not receive any study medication, baseline will be set as the last available assessment before and including day 1.

### **4.5 EFFICACY ANALYSIS**

The List of Planned Outputs (LoPO) contains the full list of reports for the efficacy analysis.

#### **4.5.1 Primary Efficacy Endpoint**

##### **4.5.1.1 Evaluation in the Treatment-Naïve Population**

For the evaluation of efficacy in the treatment-naïve population, all patients in Population A will be used.

The primary efficacy variable is the BCVA change from baseline to Week 36. The primary efficacy analysis will be performed using a Mixed Model for Repeated Measurement (MMRM) model. The model will include the categorical covariates of randomization stratification indicator for presence of RAP or PCV, treatment group, visit, and visit by treatment group interaction and the continuous covariate of baseline BCVA. An unstructured variance-covariance model will be used to account for within-patient correlation, but another variance-covariance structure, such as AR(1), may be used in case of convergence issues.

In case of a significant departure from the normality assumptions required for the MMRM, a nonparametric Mann-Whitney  $U$  test will be used to compare change from baseline between treatment arms at given visits.

The primary statistical tests will test the null hypotheses:

$H_0$ : no difference between each of the treatment group (Arms B, C, or D) and the control group (Arm A), in mean BCVA change from baseline to Week 36 vs.

$H_A$ : Arms B, C or D means are different from Arm A mean.

The model-based estimate of the difference between each of the treatment group (Arms B, C, and D) and the control group (Arm A) at Week 36, together with 95% confidence intervals and corresponding p-value will be reported as the primary efficacy measures in this population.

The mean and 95% confidence interval (CI) within each treatment group and for the difference in change from baseline between RO6867461 treatment groups (Arms B, C, and D) and the control group (Arm A) at the other time-points will also be reported. There will be no formal correction for multiple comparisons.

For the primary endpoints, a statistically significant difference at week 36 between any of the treatment Arms B, C, or D and Arm A will be concluded if the corresponding unadjusted 2-sided p-value is below 0.2.

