6.6 EFFICACY ANALYSES

6.6.1 Primary Efficacy Endpoint

6.6.1.1 Evaluation in the Treatment-Naïve Population

For the evaluation of efficacy in the treatment-naïve population, all patients in Population A will be used. Population A includes all randomized patients, with patients grouped according to the treatment assigned at randomization. For all relevant efficacy evaluation, the baseline reference will be latest non missing observation before start of study drug.

The primary efficacy variable is the BCVA change from baseline to Week 36. The primary efficacy analysis will be performed using a Mixed Model for Repeated Measurement (MMRM) model. The model will include the categorical covariates of treatment group, visit, and visit by treatment group interaction and the continuous covariate of baseline BCVA. Randomization stratification factors such as baseline BCVA (≥ 69 letters vs. ≤ 68 letters), and presence of RAP and PCV may also be incorporated in the statistical analysis as appropriate. An unstructured covariance structure will be used to account for within-patient correlation, but another variance-covariance structure may be selected in case of convergence issues. The primary statistical test will aim to test the null hypothesis (H_0) of no difference between each of the treatment group (Arms B, C, and D) and the control group (Arm A), for mean BCVA change from baseline to Week 36. The model-based estimate of the difference between each of the treatment group (Arms B, C, and D) and the control group (Arm A) at Week 36, together with 95% Confidence and corresponding p-value will be reported as the primary efficacy measures in this population. The mean and 95% confidence interval (CI) within each treatment group and for the difference between RO6867461 treatment groups (Arms B, C, and D) and the control group (Arm A) at the other time-points will also be reported. There will not be formal correction for multiple testing.

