### **2.3 DETERMINATION OF SAMPLE SIZE**

#### **2.3.1 Sample Size and Power for Treatment-Naive Population Evaluation**

The sample size for the treatment-naive population is based on the primary efficacy outcome of mean change in BCVA from baseline to Week 36. Each RO6867461 dose or dose regimen group (Arms B, C, and D) will be compared to the control group (Arm A).

Consider 68 patients randomized to Arm A and 45 randomized to each of Arms B, C, and D, with a drop-out rate of 10%. Assuming a standard deviation of 13.5 letters, this sample size would provide approximately 80% power to detect a true difference of 5.9 letters at the one-sided  $\alpha$  level of 10%. The minimum detectable difference would be approximately 3.5 letters.

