## **3. STUDY CONDUCT**

### **3.1 RANDOMIZATION**

After written informed consent has been obtained, all patients will receive a screening number assigned through the Interactive Voice and Web Response System (IxRS). After all patient eligibility requirements are confirmed on Day 1 visit the site personnel will contact the IxRS for assignment of a patient identification number (a separate number from the screening number).

Patients will be randomized in a 3:2:2:2:3 ratio to one of the study treatment arms A, B, C, D or E (see 2 for details):

Patients will be randomized on the same day the study treatment is to be initiated (Day 1 visit). After randomization and at each visit with study treatment administration (i.e., including Day 1) the IxRS will assign the appropriate study treatment kit to be used.

Randomization will be stratified for the two factors below:

- Baseline BCVA ETDRS letter score assessed on Day 1 (69 letters or better vs. 68 letters or worse)
- Presence/absence of retinal angiomatous proliferation (RAP) or polypoidal choroidal vasculopathy (PCV) at screening as assessed by the Reading Center

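### The primary MMRM gives baseline BCVA one slope for all visits; if the dependence on baseline strengthens over time, Week 36 is under-adjusted and a little precision is lost

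*SAP*

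**What the plan says.** SAP 4.5.1.1 names every fixed effect in the primary model: the "randomization stratification indicator for presence of RAP or PCV", treatment group, visit, "visit by treatment group interaction and the continuous covariate of baseline BCVA". No interaction of baseline with visit is listed. On covariance it says: "An unstructured variance-covariance model will be used to account for within-patient correlation", with a fallback under which "another variance-covariance structure, such as AR(1), may be used in case of convergence issues". The significance rule in that section applies to Week 36 only.

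SAP 3.1 stratifies randomisation by RAP/PCV and also by "Baseline BCVA ETDRS letter score assessed on Day 1 (69 letters or better vs. 68 letters or worse". The second factor is not in the SAP model. Protocol 6.6.1.1 has no baseline-by-visit term either, and says of the two stratification factors that they "may also be incorporated in the statistical analysis as appropriate".

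SAP 4.5.1.2 reuses the same model for Population C, where baseline is Week 12 (SAP 4.4.2). SAP 4.5.2 reuses it for continuous secondary endpoints.

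**The concern.** The model is flexible in the treatment effect and the covariance but rigid in the baseline effect. A patient entering at 73 letters has less room to gain than one entering at 24, and that difference may show more fully once gains have accrued. If it does, the slope of change on baseline is steeper at Week 36 than at the early visits. A single slope is a weighted average over visits, so it would be too shallow for the visit that is tested. The result would be a Week 36 contrast that corrects too little for chance baseline imbalance and has a slightly larger standard error than the same data could give. Because the model is reused, the same restriction carries into Population C and the continuous secondary endpoints.

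**Working it through.** **Inputs from the documents.** 68 patients in Arm A and 45 in each of Arms B, C and D, less 10% drop-out, give 61.2 and 40.5. SD of change is 13.5 letters, true difference 5.9, one-sided alpha 10% (all SAP 2.3.1). Entry BCVA is 24 to 73 letters (Protocol 4.2.1). BCVA is measured at nine post-baseline visits, every 4 weeks from Week 4 to Week 36 (Protocol Appendix 1).

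**Assumptions, because the documents give no figure.** Baseline SD s of 10 to 13; SD of change at Week 4 of 8, 10 or 13.5, rising linearly to 13.5; slope on baseline moving linearly from -0.10 at Week 4 to -0.30 at Week 36; three correlation patterns; and 13.5 read as the SD of change before baseline adjustment.

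**Step 1: the plan's own figure.** SE = 13.5 × √(1/61.2 + 1/40.5) = 13.5 × 0.2026 = 2.735. Power = Φ(5.9/2.735 − 1.282) = Φ(0.876) = 80.9%. Minimum detectable difference = 1.282 × 2.735 = 3.50 letters. Both agree with the plan.

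**Step 2: the slope the model fits.** With visit-specific slopes b and residual covariance R, the generalised least-squares common slope tends to b* = w′b, where w = R⁻¹1/(1′R⁻¹1). The visit SDs above are used for R, a small approximation. Visits with small variance tend to get more weight.

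**Step 3: the cost at Week 36.** With its own slope, the Week 36 residual variance is V = 13.5² − b₃₆²s². With the common slope it is V + (b₃₆ − b*)²s². In the central case (Week 4 SD 8, correlation halfway between AR(1) at 0.9 and exchangeable at 0.75), b* is about -0.10.

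- s = 10: V = 182.25 − 9.00 = 173.25. Added variance is 0.20² × 100 = 4.00, or 2.3%. SE rises by √1.023 − 1 = 1.2%. Power is Φ(5.9/(√177.25 × 0.2026) − 1.282) = 81.8%, against 82.4% with the interaction.
- s = 13: V = 182.25 − 15.21 = 167.04. Added variance is 0.20² × 169 = 6.76, or 4.0%. SE rises by 2.0%. Power is 82.3%, against 83.4%.

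**Step 4: other assumptions, same slope path.**

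| Week 4 SD | Correlation | Weight on Week 4 | b* | Added variance, s = 10 / 13 |
|---|---|---|---|---|
| 8 | AR(1) 0.9 | 0.87 | -0.124 | 1.8% / 3.1% |
| 8 | halfway | 0.72 | -0.100 | 2.3% / 4.0% |
| 8 | exchangeable 0.75 | 0.77 | -0.018 | 4.6% / 8.0% |
| 10 | AR(1) 0.9 | 0.64 | -0.153 | 1.3% / 2.2% |
| 10 | halfway | 0.51 | -0.135 | 1.6% / 2.8% |
| 10 | exchangeable 0.75 | 0.57 | -0.055 | 3.5% / 6.1% |
| 13.5 | any of the three | 0.11 to 0.37 | -0.200 | 0.6% / 1.0% |

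Over a wider grid (Week 4 SD 7 to 13.5), a Week 36 slope of -0.20 gives 0.1 to 2% and a slope of -0.40 gives 1.4 to 20%. If the slope is the same at every visit, b* equals b₃₆ and the added variance is zero. The lowest power under the planned model anywhere in that grid is 80.4%.

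**Step 5: the BCVA stratum.** The stratum is a cut of Day 1 BCVA, which is already in the model as a continuous covariate. If the relation is linear, adding the indicator gains nothing. With an assumed extra step of 2 to 6 letters at 69, it gains 0.2 to 2.7% of variance, or 0.1 to 0.7 power points.

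**The case against.** The strongest reply is that everything beyond the missing term is assumed. The documents give one SD for change to Week 36 (13.5) and one for Week 12 to Week 36 (9.7). They give no early-visit SD, no correlation between visits, no baseline SD and no slope by visit. This stands, and it limits the size of the point.

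It also rules out a stronger reading that a reader might infer: that Week 36 is in effect adjusted with the Week 4 slope. That needs the SD of change to be clearly smaller at Week 4 than at Week 36, together with particular correlations. With equal SDs, which includes a homogeneous AR(1) fallback, the fitted slope is mid-range (-0.20 in the table). With exchangeable correlation and rising SDs it moves past the Week 4 value towards zero. The direction does hold: in every case examined where the slope steepens over visits, Week 36 is under-adjusted.

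A reader might also count the omitted BCVA stratum as a second cause of lost precision, or as a departure from the protocol. Neither is supported. Continuous BCVA determines the stratum, and the protocol makes both factors optional.

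Finally, the model also affects what is implied for patients who drop out, since the primary analysis relies on missing at random (SAP 4.7). That effect was not quantified. An unstructured MMRM also conditions on each patient's earlier observed changes, and planned drop-out is only 10%. The Population C effect was not quantified either.

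**Conclusion.** The point holds as a small, optional improvement. The single slope is a fact of the SAP text. The loss is conditional on the slope strengthening over visits: about 2 to 4% of variance, 1 to 2% of the standard error, or one power point in the central case; 0.6 to 1.0% of variance for the same slopes if visit SDs are equal; and nothing if the slope is constant. These figures rest on assumed slopes, SDs and correlations, so confidence in the size is low.

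Two further inferences should be resisted. The treatment contrast is not biased with complete data, because randomisation balances baseline in expectation; only precision and the correction of chance imbalance suffer. Nor is the sample size wrong: the stated power reproduces, and the central case stays above it under the planned model.

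**What to change.** In SAP 4.5.1.1, add a baseline BCVA-by-visit interaction to the MMRM. With nine visits this is eight extra fixed-effect parameters, against 68 + 3 × 45 = 203 patients planned in Population A. In SAP 4.5.1.2, state the matching Week 12 BCVA-by-visit term; with six visits from Week 16 to Week 36 this is five parameters. Say whether the continuous secondary endpoints in SAP 4.5.2 carry the same term.

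Optionally, include the 69-letter randomisation stratum (one parameter), or add a sentence saying that continuous baseline BCVA replaces it. Little or no gain should be expected from this.

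No new data or patients are needed. The change should be written before unmasking, since adding the term afterwards would look data-driven.

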6. STATISTICAL CONSIDERATIONS AND ANALYSIS PLAN

6.1 DETERMINATION OF SAMPLE SIZE

6.1.1 Sample Size and Power for Treatment-Naive Population Evaluation

The sample size for the treatment-naive population is based on the primary efficacy outcome of mean change in BCVA from baseline to Week 36. Each RO6867461 dose

or dose regimen group (Arms B, C, and D) will be compared to the control group (Arm A).

Consider 68 patients randomized to Arm A and 45 randomized to each of Arms B, C, and D, with a drop-out rate of 10%. Assuming a standard deviation of 13.5 letters, this sample size would provide approximately 80% power to detect a true difference of 5.9 letters at the one-sided α level of 10%. The minimum detectable difference would be approximately 3.5 letters.

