### **2.3.2 Sample Size and Power for anti-VEGF-Incomplete-Responder Population Evaluation**

The sample size for anti-VEGF–incomplete-responder population is based on the primary efficacy outcome of mean change in BCVA from Week 12 to Week 36 in the subset of anti-VEGF–incomplete-responders, between Arm A and Arm E.

Consider 68 patients randomized to both Arms A and E with 65% meeting the criteria for inclusion in anti-VEGF–incomplete-responder subgroup and a drop-out rate of 10%. Assuming a standard deviation of 9.7 letters, this sample size would provide approximately 80% power to detect a true different of 4.7 letters at the one-sided  $\alpha$  level of 10%. The minimum detectable difference would be approximately 2.7 letters.

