#### **4.5.1.2 Evaluation in the anti-VEGF Incomplete Responder Population C**

For the evaluation of efficacy in the anti-VEGF–incomplete-responder all patients in the population C will be used.

The primary efficacy variable is BCVA change from Week 12 to Week 36. The primary efficacy analysis will be performed using a MMRM model described in section 4.5.1.1.

The model-based estimate of the difference in change from baseline between the treatment group (Arm E) and the control group (Arm A) means at Week 36, together with 95% Confidence and corresponding p-value will be reported as the primary efficacy measure in this population.

The mean and 95% confidence intervals within each treatment group and for the difference between RO6867461 treatment group and the control group change from baseline at the other time points will also be reported. There will be no formal correction for multiple comparisons.

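### The primary MMRM's fallback covariance has no fixed order, and its only example, homogeneous AR(1), would make the Week 36 standard error too small if the spread of BCVA change grows over time

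*SAP*

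**What the plan says.** For the treatment-naive comparison, SAP 4.5.1.1 states: "An unstructured variance-covariance model will be used to account for within-patient correlation". It then allows an exception: "another variance-covariance structure, such as AR(1), may be used in case of convergence issues". AR(1) is the only alternative named, and it is named as an example. Protocol 6.6.1.1 names none: "another variance-covariance structure may be selected in case of convergence issues". Neither document ranks the alternatives, asks for variances that differ by visit, or specifies a robust standard error for the MMRM.

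The decision rule in SAP 4.5.1.1 applies to Arms B, C or D versus Arm A at Week 36: significance is concluded if the "unadjusted 2-sided p-value is below 0.2".

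The model is reused elsewhere. SAP 4.5.1.2 says of the incomplete-responder comparison: "The primary efficacy analysis will be performed using a MMRM model described in section 4.5.1.1". SAP 4.5.2 uses it for the continuous secondary endpoints and SAP 4.5.5 for the subgroups.

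On spread, the SAP gives two figures. One is for change from baseline to Week 36 in the treatment-naive population (2.3.1): "Assuming a standard deviation of 13.5 letters". The other is for change from Week 12 to Week 36 in the incomplete-responder subset (2.3.2): "Assuming a standard deviation of 9.7 letters". No SD is given for any other visit, and no within-patient correlation.

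**The concern.** Homogeneous AR(1) has one variance and one correlation parameter for all visits. If BCVA change is less variable early than at Week 36, the fitted variance averages small early values with the larger final one. The model-based standard error at Week 36 is then too small, the p-value too low and the confidence interval too narrow, at the one visit that decides the comparison.

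There is a reason internal to the model to expect this direction. The outcome is change from baseline, adjusted for baseline BCVA. If correlation between visits fades with distance, as AR(1) itself supposes, and raw BCVA variance is stable, the baseline-adjusted variance must rise with time since baseline. A constant variance sits badly with that decay.

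An unordered, permissive fallback also leaves the structure behind a primary p-value to be chosen after results have been seen.

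**Working it through.** **Inputs from the documents.** 68 versus 45 patients with 10% dropout, so 61.2 versus 40.5; SD 13.5 at Week 36; one-sided 10%, which has the same critical value (1.2816) as two-sided 20%; nine post-baseline BCVA visits, Weeks 4 to 36 (schedule of assessments).

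**Inputs assumed.** The SD at every visit before Week 36, and the within-patient correlations.

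**Step 1: the plan's own figure.** SE = 13.5 × √(1/61.2 + 1/40.5) = 2.735. Minimum detectable difference = 1.2816 × 2.735 = 3.50 letters. Power for 5.9 letters = Φ(5.9/2.735 − 1.2816) = 80.9%. The stated 3.5 letters and approximately 80% reproduce.

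**Step 2: error under AR(1) with model-based SE.** With complete data the AR(1) variance is approximately the mean of the visit variances. Let r = √(mean visit variance)/13.5. The actual two-sided error is 2 × [1 − Φ(1.2816 r)], and coverage of a nominal 95% interval is 2Φ(1.96 r) − 1. Example: a linear path from 9 to 13.5 has mean 11.25 and step 0.5625, so mean variance = 11.25² + 0.5625² × (9² − 1)/12 = 128.67, pooled SD 11.34 and r = 0.840.

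| Assumed SD path | Pooled SD | r | Error at the 20% rule | 95% CI coverage |
|---|---|---|---|---|
| 13.5 throughout | 13.50 | 1.000 | 20.0% | 95.0% |
| 12 to 13.5, linear | 12.76 | 0.945 | 22.6% | 93.6% |
| 11 to 13.5, linear | 12.28 | 0.909 | 24.4% | 92.5% |
| 9 to 13.5, linear | 11.34 | 0.840 | 28.2% | 90.0% |
| 7 to 13.5, linear | 10.46 | 0.775 | 32.1% | 87.1% |
| 9 at Week 4, flat at 13.5 from Week 12 | 12.84 | 0.951 | 22.3% | 93.8% |
| 15 falling to 13.5, linear | 14.26 | 1.056 | 17.6% | 96.2% |

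**Step 3: simulation check.** REML AR(1) fits were simulated with 68 versus 45 patients, 10% random dropout, three true correlation patterns and 600 runs each (Monte Carlo error about 1.6 points). Model-based error was 20% to 22% with constant SD, 22% to 26% from SD 11, 27% to 29% from SD 9, 30% to 34% from SD 7, and 21% to 24% with the Week 12 plateau. With sandwich standard errors on the same fits, the error over all scenarios was 17% to 24%, scattered around 20%.

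**Step 4: a second route.** Take raw BCVA with constant variance and correlation ρ^k at k four-week steps, adjust for baseline, and fit the best AR(1) by likelihood over nine visits. For an assumed ρ of 0.70 to 0.95, r runs from 0.935 to 0.781 and the error from 23% to 32%. If 10% or 20% of the variance is measurement noise, the error is 22% to 27% or 22% to 25%.

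**Step 5: where a fallback could be triggered.** An unstructured covariance over k visits has k(k + 1)/2 parameters.
- BCVA, Population A: 9 visits, 45 parameters.
- SD-OCT, Population A: 11 visits, 66 parameters.
- BCVA, Population C (baseline at Week 12): 6 visits, 21 parameters.
- FFA areas (post-baseline at Weeks 12 and 36 only): 2 visits and 3 parameters in Population A; a single visit in Population C.

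The small subgroups and the SD-OCT models are therefore the most plausible places for non-convergence.

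**The case against.** The plan's analysis is unstructured, and AR(1) is only an example. A heterogeneous structure with robust standard errors is already allowed by the wording. Harm needs three things together: a failed unstructured fit, AR(1) with model-based standard errors, and variance that rises towards Week 36. The first looks rare for the main comparisons: unstructured fits to idealised simulated data (normal, 10% dropout, an EM algorithm) converged in 300 of 300 runs for each of Population A, Population C and SD-OCT. Subgroups were not tested. The study also describes itself as hypothesis-generating. All of this stands, and it limits the point to a conditional one.

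A reader might infer from 9.7 and 13.5 letters that the documents themselves show the spread growing. They do not. The two SDs cover different intervals in different populations. Even ignoring the population difference, they fit a Week 12 SD of √(13.5² − 9.7²) = 9.4 letters if early and late changes are uncorrelated. They equally fit one already at 13.5 if that correlation is −9.7/(2 × 13.5) = −0.36.

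The latitude of the wording is not a full defence. It permits a sound choice but does not require one, and the only structure it names is the one with the equal-variance constraint.

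**Conclusion.** The point holds conditionally and is a cheap improvement rather than a flaw in the primary analysis. If homogeneous AR(1) with model-based standard errors replaced the unstructured model, and the SD rose linearly from 12 to 7 letters at Week 4 to 13.5 at Week 36, the two-sided error for Arms B, C or D versus A would be about 22% to 32% instead of 20%. An early plateau gives about 22%, a constant SD gives 20% and a falling SD gives less.

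Two stronger readings are tempting and not supported. One is that the plan will inflate its error rate: that requires non-convergence and an SD path that the documents do not give. The other is that the 20% rule is at risk in the same way for Arm E versus Arm A: SAP 4.5.1.2 carries the model over but states no significance threshold, and Population C's smaller covariance matrix makes the trigger less likely. Any narrowing of intervals would still apply there if the fallback were used.

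**What to change.** In SAP 4.5.1.1, replace the open fallback with a fixed order: unstructured; then heterogeneous Toeplitz; then heterogeneous AR(1); then heterogeneous compound symmetry. Use the first that converges. State that homogeneous AR(1) is not used, and that any structured covariance is reported with empirical (sandwich) standard errors and a small-sample correction. Say that this applies to every analysis that refers to this MMRM: Population C, the continuous secondary endpoints, the covariate sensitivity analyses and the subgroups.

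The cost is SAP wording. Results do not change where the unstructured model converges. Where a fallback is needed, the interval may be slightly wider. The small-sample correction matters most in small subgroups, where uncorrected sandwich standard errors can themselves be too small. Other orders are defensible; what matters is that one is fixed in advance and lets the variance differ by visit.
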